4.2.3 EXPLORATORY ENDPOINTS

The exploratory endpoints include assessment of changes in composition and distribution of blood-based and CSF (in consenting subjects) biomarkers, as well as changes in imaging results as measured by vMRI, fMRI, and ASL.

The serial compositional analysis of individual subject's plasma will be performed to identify specific biomarkers associated with cognitive functional changes and/or indicators of AD progression. DNA will be extracted from blood samples to explore epigenetic changes. In addition, subjects who consent to participate in the optional CSF biomarker research will undergo two lumbar punctures for CSF collection, the first occurring prior to initial dosing, and the second occurring following final dosing. The CSF will be utilized to assess the potential therapeutic effects of GRF6019 on AD biomarkers of neuronal death, synaptic function, inflammation, and growth factors.

5.1 INCLUSION CRITERIA

In order to be eligible for inclusion, all subjects must meet the following criteria:

- Male or female, aged 60-90 years (inclusive).
- Diagnosis of probable AD based upon the National Institute on Aging-Alzheimer's Association (NIA-AA) Criteria.
- MMSE Score 12-24 inclusive.
- Modified Hachinski Ischemia Scale (MHIS) score of ≤ 4 .
- Have a dedicated, reliable and competent trial partner (e.g., caregiver or family member) who has frequent contact with the subject (defined as approximately 10 hours per week) who is willing to provide support to the subject to ensure compliance with study requirements. The trial partner should understand the nature of the study and be willing to complete the trial partner scales and functional assessments throughout the study.
- The subject (with support of a trial partner) must be able to follow the study protocol, receive the treatment in the established timeframe, and continue during the follow-up interval.
- The subject and trial partner must be sufficiently fluent in English and have visual and auditory acuity sufficient to be capable of reliably completing all study assessments.

- Provided a signed and dated informed consent form (either the subject and/or subject's legal representative as well as the trial partner) in accordance with local regulations/guidelines/IRB/IEC.
- Adequate renal function as defined by estimated glomerular filtration rate (eGFR) ≥ 45 mL/min/1.73 m² using the Modification of Diet in Renal Disease (MDRD) study equation ([MDRD for Adults \(Conventional Units\) | NIDDK, n.d.](#)).
- Systolic ejection fraction of $\geq 55\%$ on trans-thoracic echocardiogram.
- Willing to spend up to 7 nights in an inpatient study unit during both dosing periods.

In order to be eligible for inclusion in the optional CSF biomarker research, all subjects must meet the following criteria:

- Currently enrolled in the ALK6019-201 study.
- Provided a signed and dated informed consent form for CSF collection (either the subject and/or subject's legal representative) in accordance with local regulations/guidelines/IRB/IEC.
- Not yet dosed in the ALK6019-201 study.

5.2 EXCLUSION CRITERIA

A subject will not be eligible for inclusion if any of the following criteria apply:

- Positive screening for Hepatitis B, Hepatitis C, or Human Immunodeficiency Virus (HIV).
- Evidence of clinically relevant neurological disorder(s) other than AD.
- History of blood coagulation disorders or hypercoagulability; any concurrent use of an anticoagulant therapy. (e.g., heparin, warfarin, thrombin inhibitors, Factor Xa inhibitors). Use of antiplatelet drugs (e.g., aspirin or clopidogrel) is acceptable.
- Initiation or change in the dosage of cholinesterase inhibitors (AChEI), memantine, Axona, vitamin E supplementation, or selegiline within 3 months prior to screening.
- Prior hypersensitivity reaction to any human blood product or intravenous infusion; any known clinically significant drug allergy.
- Treatment with any human blood product, including transfusions and intravenous immunoglobulin, during the 6 months prior to screening.
- History of immunoglobulin A (IgA), haptoglobin or C1 inhibitor deficiency; stroke, anaphylaxis, or thromboembolic complications of intravenous immunoglobulins.
- Heart disease, including myocardial infarction, unstable, new onset or severe angina, or congestive heart failure (New York Association Class II, III or IV) in the 6 months prior to dosing;
- Poorly controlled high blood pressure (systolic blood pressure of 160 mmHg or higher and/or diastolic blood pressure of 100 mmHg or higher) despite treatment during the 3 months prior to dosing, or treatment refractory high blood pressure, defined as treatment requiring 3 or more antihypertensives from different classes.
- History of Torsades de Pointes dysrhythmia or hypocalcemia of any kind, including secondary to absorption syndromes secondary to gastric bypass surgery.
- Current or chronic history of liver disease or known hepatic or biliary abnormalities (with the exception of Gilbert's syndrome or asymptomatic gallstones).
- Uncontrolled diabetes defined as HbA1c $> 7.5\%$ or requiring insulin.
- Clinically significant abnormalities in complete blood count, complete metabolic panel, serum albumin, serum lipids, blood coagulation tests, or the levels of thiamine, pyridoxine, cobalamin and thyroid stimulating hormone.

- Hemoglobin < 10 g/dL in women and < 11 g/dL in men.
- Urine protein-to-creatinine ratio (UPCR) of > 1.5 grams of protein per gram of creatinine.
- Clinically significant abnormalities on screening electrocardiogram (ECG) including QTc intervals (using Fridericia's correction formula) of ≥ 450 ms in men and ≥ 470 ms in women.
- Clinically significant abnormalities on echocardiogram.
- Inadequate venous access to allow IV drug delivery or multiple blood draws.
- Concurrent participation in another interventional clinical trial. Prior clinical trial subjects must have been off study agents for at least 30 days (or 5 half-lives, whichever is longer), 4 months for disease modifying therapies, and 1 year for vaccine or immunotherapy trials prior to screening.
- Concurrent daily treatment with benzodiazepines, long-acting opioids, or other medications that, in the investigator's opinion, interfere with cognition. [Note: intermittent treatment with low-doses of shorter half-life benzodiazepines (e.g. lorazepam, alprazolam) may be permitted, provided that no dose is administered within the 72 hours preceding any cognitive assessment].
- A history of a major psychiatric disorder diagnosed before the onset of AD, including schizophrenia, major depression or bipolar disorder, and/or alcohol/substance dependency. Psychiatric symptoms that occur in the context of AD (e.g. psychosis, irritability, depression) are not exclusionary unless the PI believes they could interfere with study procedures.
- Active suicidal ideation with at least some intent to act, with or without a specific plan, in the past 6 months.
- Presence of a pacemaker or any other implant that would be a contraindication to an MRI exam or claustrophobia that would not enable the subject to undergo an MRI.
- >2 lacunar strokes or other imaging abnormality on baseline MRI that would make the interpretation of subsequent MRI scans of the brain difficult.
- Any other condition and/or situation that the investigator believes may interfere with the safety of the subject, the intent and conduct of the study, or interpretation of study data.

A subject will not be eligible for inclusion in the optional CSF biomarker research if any of the following criteria apply:

- Allergy or sensitivity to lidocaine or other local anesthetics to be used for the lumbar puncture.
- Skin infection near the site of the lumbar puncture.
- Suspicion of cord mass or signs of cord compression.
- Suspicion of intracranial mass or raised intracranial pressure (e.g., as evidenced by papilledema).
- Altered mental status (from baseline).
- Use of oral antiplatelet therapy (e.g. clopidogrel, prasugrel, ticagrel) within 5 days prior to the lumbar puncture. Use of aspirin is permitted.

5.3 STRATEGIES FOR RECRUITMENT AND RETENTION

We do not anticipate any particular challenges in meeting recruitment goals of enrolling a total of 20 subjects per group in this study. Similarly, as AD has a higher prevalence in women, we do not anticipate difficulties in enrolling female subjects. Subjects will be recruited continuously until the desired sample size is achieved. Subjects who withdraw or are withdrawn during screening or prior to completing Visit 8 may be replaced to enroll sufficient evaluable subjects.

We expect enrollment in this trial to be consistent with the observation that typically the majority of subjects enrolled in clinical trials conducted in the United States are non-Hispanic whites. If the risk/benefit analysis of GRF6019 justifies larger subsequent trials, special efforts will be made to enroll subjects from diverse ethnic and racial groups.

This trial is enrolling subjects with AD who may have sufficient cognitive impairment to be considered a vulnerable population. In this situation, the subject’s agreement to participate in the study will still be obtained to their best level of his or her understanding, and recruitment will not proceed if the subject refuses, shows significant distress or the trial partner and/or legally authorized representative refuse. For subjects who are, in the opinion of the investigator, unable to give informed consent, consent will be obtained from the legally authorized representative. Subjects will receive a modest stipend for participation in the study.

The expected length of participation in the study, seven months, is not expected to be unduly onerous on subjects or their trial partners. During the two treatment periods at weeks 1 and 13, subjects will be housed in inpatient clinical trial units. If the trial partner does not reside within a reasonable distance from the inpatient facility, they will be given the option to stay with the subjects or to stay in a nearby hotel/motel. Financial support for meal and miscellaneous expenses may be provided as appropriate (it is expected that meals will be provided by the study facilities as needed). Use of visit transport services and study buddies (registered and trained personnel that can stand in for the trial partner for required visits) may also be incorporated into the trial to support both the subject and their trial partner in maintaining study visit compliance.

A description of the clinical trial will be posted on clinicaltrials.gov that will provide additional transparency to the public and possibly aid study recruitment. In addition, advocacy groups and patient networks will be approached for recruitment as needed.

5.4 SUBJECT WITHDRAWAL OR TERMINATION

5.4.1 REASONS FOR WITHDRAWAL OR TERMINATION

A subject will be withdrawn from the study for the following medical or administrative reasons:

- Occurrence of a treatment-emergent AE that represents an unacceptable risk to the subject and when continued participation in the investigational study is not warranted, in the judgment of the investigator. The investigator must follow the subject until the AE resolves or is stable, unless the subject is lost to follow up.
- Subject and/or trial partner noncompliance, defined as refusal or inability to adhere to the trial schedule or procedures.
- At the request of the subject or the subject’s legally authorized representative (e.g., subject withdraws consent), investigator, Sponsor, or regulatory authority.
- Pregnancy.

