5.4.2 HANDLING OF PARTICIPANT WITHDRAWALS OR TERMINATION

Subjects will be encouraged to complete the study and all assessments. However, subjects may voluntarily withdraw at any time, and the investigator may discontinue individual subjects from the study at any time.

Approximately 40 subjects (approximately 20 in the 100 mL group and 20 in the 250 mL group) will be enrolled in the study with the intent of obtaining at least 30 evaluable subjects who have received at least 5 doses and completed through Visit 8.

Subjects who have received at least one infusion but are withdrawn or withdraw from the study will be encouraged to complete the end of study procedures within 4-6 weeks of their last visit. For post-study AE and SAE reporting, see [Section 8.3.1](#). The primary reason for study discontinuation will be documented on the case report form (CRF).

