8.4 REPORTING PROCEDURES

8.4.1 ADVERSE EVENT REPORTING

All subjects who have given informed consent will be evaluated for AEs. All AEs that occur after the time of treatment with the study agent will be considered Treatment Emergent AEs. Subjects with Treatment-Emergent AEs must be followed until the AE is resolved or is stable, unless the subject is lost to follow up.

Each AE or suspected adverse reaction must be described as follows: the date of onset, date of resolution, severity (mild, moderate, severe), frequency of the event (single episode, intermittent, continuous), action taken with study treatment (no action taken, treatment held, treatment discontinued), outcome, causality* (unrelated, possibly related, definitely related), and seriousness criteria. Each AE or suspected adverse reaction must be recorded separately.

***Note:** Causality assessment will be made only when the AE occurs after the subject has initiated at least one infusion of the study agent. An AE occurring before the subject’s exposure to study agent will always be labeled as “unrelated”.

Any AE occurring during the study must be documented in the subject’s medical records and as an AE in the CRF. Any SAE occurring during the study must be documented in the subject’s medical records and as an SAE in the CRF.

A separate set of SAE pages should be used for each SAE. However, if at the time of initial reporting, multiple SAEs are present that are temporally and/or clinically related, they may be reported on the same SAE page.

The investigator should attempt to establish a diagnosis of the event (that meets the definition of an AE or SAE) based on signs, symptoms, and/or other clinical information. In such cases, the diagnosis should be documented as the AE and/or SAE and not the individual signs or symptoms. The diagnosis will become the basis for the verbatim term as reported by the investigator. If no diagnosis is known and clinical signs and symptoms are not present, the abnormal finding should be recorded.

In addition to the investigator’s own description of the AE, each AE will be encoded according to the MedDRA.

The investigator will take all appropriate and necessary therapeutic measures required for resolution of the AE. Any medication necessary for the treatment of an AE must be recorded on the concomitant medication CRF.

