8.4.4 REPORTING OF PREGNANCY

While pregnancy itself is not considered an AE, pregnancy occurring in a clinical study must be followed to collect information regarding the experiences of gestation and pregnancy with study agent exposure. The investigator must report any pregnancy that occurs in a female study subject subsequent to first exposure to the study agent until End of Study, or 3 months following a subject's last dose. All pregnancies will be reported to the IRB, Sponsor, and CRO. In the event of a pregnancy, treatment will be discontinued, and the subject will undergo continued safety follow-up through pregnancy outcome.

Any pregnancy must be followed by the investigator until delivery or to the end of pregnancy. Any anomalies, complications, abnormal outcomes, or birth defect observed in the child must be reported as an SAE within 24 hours of the investigator or study personnel's first knowledge.

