13.3 PROTOCOL DEVIATIONS

A protocol deviation is any noncompliance with the clinical trial protocol or with GCP. The noncompliance may be either on the part of the subject, the investigator, or the study site staff. When deviations occur, corrective actions are to be developed by the site and implemented promptly.

These practices are consistent with ICH E6:

- 4.5 Compliance with Protocol, sections 4.5.1, 4.5.2, and 4.5.3
- 5.1 Quality Assurance and Quality Control, section 5.1.1
- 5.20 Noncompliance, sections 5.20.1, and 5.20.2.

Protocol Deviations will be categorized as either Major or Minor and will be defined in the study-specific Protocol Deviation Plan.

Major Protocol Deviations are departures from the approved protocol relating to the conduct of the study which may affect the rights, safety and/or wellbeing of study participants, or the study outcomes or data quality. Major Protocol Deviations may result in data that are not deemed evaluable for the per protocol analysis and/or may require that subjects be discontinued from the study. Major Protocol Deviations are Significant Clinical Issues.

Minor Protocol Deviations are departures from the approved protocol relating to the conduct of a study that does not affect the rights, safety and/or wellbeing of study participants, or the study outcomes or data quality. Minor Protocol Deviations do not require review by the medical monitor. Minor Protocol Deviations would not generally preclude subject data from the per protocol analysis population.

Note: persistently missed or incomplete study procedures and/or study evaluations will be considered Major Protocol

Deviations.

All deviations will be logged and tracked by the site and CRO. Periodic review of Protocol Deviations will inform assessment of site performance.

It is the responsibility of the site to use continuous vigilance to identify and report deviations promptly to the study CRO and/or Sponsor. All deviations must be addressed in study source documents. Protocol Deviations must be sent to the local IRB per their guidelines. The site PI/study staff is responsible for knowing and adhering to their IRB requirements.

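### The mandatory withdrawal rule in Protocol 5.4.1 can be read to remove a subject who declines only the Week 13 infusions, and 5.4.1–5.4.2 give no general path to stop infusions but keep the scheduled visits

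*Protocol*

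**What the plan says.** Protocol 5.4.1 is written as an obligation: "A subject will be withdrawn from the study for the following medical or administrative reasons". One listed reason is "Subject and/or trial partner noncompliance, defined as refusal or inability to adhere to the trial schedule or procedures". The adverse-event reason is softer because it adds a second test: "and when continued participation in the investigational study is not warranted, in the judgment of the investigator". The Week 13 infusions belong to the schedule under Protocol 6.1.7, 7.3.4 and Section 17.

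Protocol 5.4.2 begins with "Subjects will be encouraged to complete the study and all assessments". Subjects who leave after at least one infusion "will be encouraged to complete the end of study procedures within 4-6 weeks of their last visit", and 7.3.7 likewise offers only the end-of-study assessments. Section 13.3 says that major deviations "may require that subjects be discontinued from the study". For pregnancy, 8.4.4 says that "treatment will be discontinued, and the subject will undergo continued safety follow-up through pregnancy outcome".

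Other text treats stopping drug and leaving the study as different events. Protocol 8.4.1 records discontinuation of treatment as an action taken for an adverse event. Protocol 10.4.5 plans to compare subjects who complete both dosing series with those who complete only the first. SAP 4.1 tabulates discontinuation of study drug apart from discontinuation of the study. These are reporting categories and do not tell a site what to do.

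After exit, 8.3.1 places no duty on the investigator to seek serious events. It encourages notice of possibly related events within 30 days. SAP Section 5 excludes early-termination results from the tabulated efficacy summaries.

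**The concern.** A subject who has had five infusions and does not want another inpatient week is a case the plan itself foresees. Read literally, 5.4.1 turns that choice into study withdrawal, even if the subject and trial partner would come to every outpatient visit. Sections 5.4.2 and 13.3 can be read more leniently, so follow-up of the same kind of subject could differ between sites.

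Two outputs are touched. TEAE incidence is a primary endpoint, reported as a percentage of the Safety Set (SAP 6 and 6.1.5). The withdrawn subject stays in that denominator with fewer calendar days of scheduled review. In the efficacy tables the subject remains in the Evaluable Set, having received five doses, but contributes nothing at Days 112, 140 or 168, even after attending the exit assessment. Such a subject is also past Visit 8, so the replacement rule in Protocol 10.5 does not apply.

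**Working it through.** **The plan's own figure.** 40 × (1 − 0.25) = 30 evaluable subjects, as the Protocol Summary states. For sample size, evaluability is reached at Visit 8 (Day 6), so a refusal at Week 13 does not change it.

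**Inputs.** Visit 10 is at Day 56 and Visit 11 at Day 85. The exit assessment is 4–6 weeks (28–42 days) after the last visit. Study end is Day 168. The last first-series infusion is on Day 5 and the last second-series infusion on Day 89. There are 20 subjects per group. Days are nominal, and the exit assessment is assumed to take place.

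**Formulas.** Exit = last visit + 28 to + 42. Gap = 168 − exit. Share = gap ÷ (168 − last visit). Person-day share = gap ÷ (20 × 168) = gap ÷ 3,360.

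| | Last visit Day 56 | Last visit Day 85 |
|---|---|---|
| Exit | Day 84–98 | Day 113–127 |
| Days to 168 with no scheduled review | 84–70 of 112 (75–63%) | 55–41 of 83 (66–49%) |
| Share of 3,360 person-days | 2.5–2.1% | 1.6–1.2% |
| End of 30-day encouraged reporting | Day 114–128 | Day 143–157 |
| Days left after that | 54–40 (48–36%) | 25–11 (30–13%) |
| Follow-up after the Day 5 infusion | 79–93 days | 108–122 days |

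**Comparison with a completer.** 168 − 89 = 79 days after the last infusion. On nominal days, the decliner's follow-up after the last dose is equal or longer. At the early edge of the Visit 10 window (Day 49), exit is Day 77–91 and follow-up is 72–86 days, so the shortest case is 7 days under the nominal 79.

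**Number of subjects.** The documents give no rate of declining Week 13. If one to three per group of 20 are assumed, the loss runs from 41 ÷ 3,360 = 1.2% to 3 × 84 ÷ 3,360 = 7.5% of that group's scheduled person-days.

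**Counts that do not move.** The 24-week tolerability count (Protocol 4.2.1) already requires at least 10 infusions, so a Week 13 decliner fails it whether retained or not.

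**The case against.** The strongest reply is that 5.4.1 may not be aimed at this subject at all. Protocol 4.2.2 and 10.4.5 list infusions separately from schedule and procedures, 13.3 is permissive, and 5.4.2 encourages completion of all assessments. That stands as far as it goes: the broad reading is plausible but not certain. A reader might infer that the protocol definitely ejects everyone who declines infusions, and the documents do not support that. They permit both readings, and that ambiguity is the reason to clarify.

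A reader might also infer that safety follow-up after dosing is cut short. On nominal days it is not, as the comparison with a completer shows. What is lost is late calendar time, in which new-onset events could still occur.

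Nor is pregnancy the only case with continued follow-up. Protocol 5.4.1 requires follow-up of the adverse event behind a withdrawal, and 8.4.1 requires follow-up of every existing TEAE to resolution or stability. Those duties cover existing events and do not keep the scheduled visits.

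Finally, adverse events are mostly not formally tested and efficacy is descriptive and unpowered. Exit scores remain in the ITT listings, and it is defensible to keep a Day 84–98 score out of a Day 168 row. The per-period TEAE tables and the Kaplan-Meier curves in SAP 4.9 would show that follow-up was shortened. These facts limit the consequence, but they do not restore the data.

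**Conclusion.** The point holds as a gap in conduct wording, and closing it is a cheap improvement. Protocol 5.4.1 can be applied to a subject who declines only Week 13, and 5.4.1–5.4.2 provide no general route to stop infusions and stay. Each subject so withdrawn leaves 41–84 days unobserved and has one untabulated exit assessment in place of three scheduled visits. The size rests on a last visit between Day 56 and Day 85, nominal visit days, an exit assessment that is actually attended, and a site that reads the rule strictly. The number of subjects is unknown. The main loss is Day 112–168 cognitive and functional data, followed by late new-onset adverse events. A reader might infer a bias between the two doses, but nothing in the documents gives it a direction and none is claimed.

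**What to change.** **Protocol 5.4.1–5.4.2.** Define discontinuing study agent separately from withdrawing from the study. State that declining or stopping infusions is not by itself noncompliance requiring withdrawal. Ask these subjects to keep the remaining non-infusion visits, or at least AE/SAE contacts on those dates, to Day 168. The exceptions are withdrawn consent, loss to follow-up, or an investigator's judgment that the visits themselves are unwarranted.

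**SAP Section 5.** Tabulate these subjects' efficacy results at the scheduled visits, with the number of infusions received shown.

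**SAP 6.1.3.** Events are allocated by period start and stop, and the text states no Period 2 start for a subject with no infusion 6. Say that all such a subject's TEAEs count in the overall table and either in Period 1 or in a separate off-treatment row, and not in Period 2.

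**Cost.** A short amendment and two SAP rules, with no new visits or procedures. A few subjects and trial partners carry the visit burden and may decline it. Later summaries would mix 5- and 10-infusion subjects, which is why infusions received should be displayed. Nothing is recovered from subjects who withdraw consent or are lost.
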